6.3 Missing Data Conventions

Except in the cases specified, missing data will not be replaced.

6.4 Definition of the baseline

Baseline measurements will be the last measurement taken prior to inclusion or the last measurement taken prior to the first administration of treatment.

6.5 Statistics

The confidence intervals provided will be two-sided 95% confidence intervals except for the primary endpoint where the calculated confidence interval will be a one-sided 95% confidence interval.

Quantitative data will be described using the following descriptive statistics: number, mean, standard deviation, median, first and third quartile, and minimum and maximum. These statistics will be considered the usual statistics for the analysis of quantitative variables. Quantitative variables can be categorized using their median or a cut-off known from the medical literature.

Categorical variables will be summarized, using the following descriptive statistics: the number, frequencies and percentages for each level of the variable. These statistics will be considered as the usual statistics for the analysis of categorical variables.

When necessary, the 95% confidence intervals for the proportions can be calculated from the exact binomial distribution.

Survival data will be estimated and plotted using the Kaplan Meier method (Kaplan and Meier, 1958). They will be described by the median and rates calculated at different time points with their two-sided 95% confidence intervals. The confidence intervals for the rates will be constructed from the Greenwood variance calculated using the log-log transformation.

The median follow-up time will be estimated by the reverse Kaplan-Meier method (Shemper, 1996).

As an exploratory measure, for the uni and multivariate analyses, the hazard ratios will be estimated using a Cox model (Cox, 1984). The hypothesis of proportionality of the rates will be tested using the graphical representation and the test based on Schöenfeld's residuals (Grambsch, 1994); the linearity of the effect of the continuous variables on the risk will be evaluated from the graphical representation of the martingale residuals. Confidence intervals for the coefficient estimates of the Cox models will be calculated using the Wald method.

7 Statistical analysis

	Population ITT	Population ITTm	Tolerance population	Population Per protocol
Description of Baseline				
Eligibility criteria for inclusion	X	X		X
Demographic characteristics	X	X		X
Clinical characteristics at inclusion	X	X		X
Biological characteristics at inclusion	X	X		X
Characteristics related to the disease	X	X		X
Median follow-up time	X	X		X
Main criterion				
Progression-free survival rate at 9 months	X	X		X
Secondary criteria				
Overall survival, progression-free survival	X	X		X
Progression-free survival at 9 months	X	X		X
Response rate (RECIST) at 9 months	X	X		X
Response rate (EASL) at 9 months (centralized review)	X	X		X
Secondary resection rate	X	X		X
Evolution of tumor marker levels	X	X		X
Tolerance				
Administration of the treatment (duration, dose received ...)			X	
Toxicities			X	
Exploratory analysis	X	X		X

7.1 Patient characteristics at inclusion

7.1.1 Inclusion Characteristics - Eligibility

Population: ITT

Patient eligibility at inclusion will be described by:

- Number and percentage of patients who met all inclusion criteria
- Number and percentage of patients who met all non-inclusion criteria
- Number and percentage of patients who met all inclusion and non-inclusion criteria

7.1.2 Demographic characteristics

Population: ITT

The following characteristics at inclusion will be described:

- Age (years);
- Inclusion center (number of patients included per center);

- Gender (Male vs Female).

7.1.3 Clinical characteristics

Population: ITT

The following characteristics at inclusion will be described:

- Weight (kg);
- General WHO status (0 vs 1 vs 2);
- Score by Köhne.

Definition:

Bottom:

- WHO 0-1 and a single metastatic tumor site

Intermediate:

- WHO 0-1 and more than one metastatic tumor site and PAL \leq 300 U/L
- WHO >1 and white blood cells $\leq 10 \times 10^9 /L$ and a single metastatic tumor site

High :

- WHO 0-1 and more than one metastatic tumor site and PAL > 300 U/L
- WHO >1 and white blood cells $> 10 \times 10^9 /L$
- WHO >1 and white blood cells $\leq 10 \times 10^9 /L$ and more than one tumor site

7.1.4 Biological characteristics

- Leukocytes ($/mm^3$);
- Albumin ($\mu\text{mol}/L$);
- PAL (U/L);
- ACE ($\mu\text{g}/L$);
- CA19-9 (U/mL).

7.1.5 Characteristics related to the disease

Population: ITT

The following characteristics at inclusion will be described:

- Time from cancer diagnosis to inclusion date (months)
- Location of the primary tumor
- Metastatic location (for liver metastases, right lobe/left lobe and number of liver metastases, presence of lung metastases)
- History (diabetes, hypertriglyceridemia, hypercholesterolemia, hypertension, other (a list will be provided))
- Concomitant treatments (statin, fibrate, anti-coagulant, anti-hypertensive, aspirin, other (a list will be provided))
- KRAS status
- Performance of a PET scan (presence of pulmonary metastases, locoregional lymph nodes, other ...)
- Previous treatment and description of the type of treatment (RCT, CT, surgery, radiofrequency ...)

7.2 Monitoring characteristics

7.2.1 Definition of median follow-up time

Population: ITT

Median follow-up time is defined as the time interval between the date of inclusion and the date of last news (patients alive or lost to follow-up) or for deceased patients, the date of death (regardless of cause).

7.2.2 Evaluation of the median follow-up time

The median follow-up time (for living patients) and its 95% confidence interval will be calculated in months. It will be estimated by the inverse Kaplan Meier method.

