Taking into account a rate of 20% of patients lost to follow-up or not evaluable, **58 patients should be included**.

At the end of recruitment:

During analysis:

- if 32 or fewer patients are alive without progression, then the treatment is considered ineffective
- if 33 or more patients are alive without progression, then the treatment is considered effective

The decision rule will be adjusted based on the actual number of evaluable patients.

XII.4 Statistical analysis plan

Analysis Populations:

Patients included in the study will be described on an intention-to-treat (ITT) basis as well as patients not evaluable for the primary endpoint.

A patient is considered evaluable if he or she has had chemoembolization and received at least one cycle of chemotherapy and for whom we have at least one evaluation during the 9 months of follow-up.

All efficacy analyses will be performed on a modified intention-to-treat basis (evaluable patients) included in the study regardless of eligibility criteria and treatment received.

Tolerability population: the ITT population that received at least one dose of the treatments.

In all cases of discontinuation, the patient remains in the intention-to-treat analysis. There is no exclusion period for a subsequent therapeutic trial.

Key analyses:

A statistical analysis plan will be written prior to freezing the database.

The description of clinical and medical variables will be done using percentages (95% confidence interval) for qualitative variables and mean (standard deviation) and median (Min-Max) as well as inter-quartile range (Q1-Q3) for quantitative analysis.

Survivals and times will be estimated by the Kaplan Meier (KM) method. They will be described by medians and rates at different time points with their 95% confidence intervals.

Median follow-up time will be calculated using the reverse Kaplan Meir method.

The time to onset of grade 3/4/5 toxicity will be estimated using the Kaplan Meier method.

Exploratory Analyses:

- research into factors predictive of progression-free survival and/or overall survival

XII.5 Independent Committee Supervisory Committee

An independent committee composed of 1 clinician / 1 methodologist / 1 pharmacovigilant expert will be formed before the start of the trial.

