4.3 Justification of the number of subjects needed

A 1-step Fleming design was used, with a one-sided α risk of 5% and a power ($1-\beta$) of 90%.

The clinical assumptions made were:

H_0 : A 55% progression-free live proportion during the first 9 months is unattractive;

H_1 : A proportion of patients alive without progression of more than 55% during the first 9 months would show the interest of the treatment; a proportion of 75% is hoped for.

48 evaluable patients were required. Taking into account a 20% rate of patients lost to follow-up or not evaluable, 58 patients were to be included.

The decision rules are as follows: of the 48 evaluable patients

- If 32 or fewer patients are alive without progression, then the treatment is considered ineffective
- If 33 or more patients are alive without progression, then the treatment is considered effective

The decision rule will be adjusted based on the actual number of evaluable patients.

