5.1 Definition of analysis populations

5.1.1 Intent-to-treat (ITT) population

The intention-to-treat population is defined as all patients included in the study, regardless of eligibility criteria.

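### Read literally, SAP 7.2.2 limits the reverse Kaplan-Meier median follow-up to living patients, which turns it into the survivors' plain median and understates follow-up under staggered entry

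*SAP*

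**What the plan says.** SAP 7.2.2 gives the instruction: "The median follow-up time (for living patients) and its 95% confidence interval will be calculated in months". Its next sentence names the estimator: "It will be estimated by the inverse Kaplan Meier method".

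The related text carries no restriction to living patients:

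- SAP 7.2.1, headed with the ITT population, runs follow-up from inclusion to the "date of last news (patients alive or lost to follow-up) or for deceased patients, the date of death (regardless of cause").
- SAP 5.1.1: "The intention-to-treat population is defined as all patients included in the study, regardless of eligibility criteria".
- SAP 6.5: "The median follow-up time will be estimated by the reverse Kaplan-Meier method".
- Protocol XII.4: "Median follow-up time will be calculated using the reverse Kaplan Meir method".
- The table at the start of SAP section 7 assigns median follow-up to the ITT, modified ITT and per-protocol populations. None of these is defined by vital status.

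Neither document explains the parenthesis in 7.2.2. Neither states which patients count as events and which as censored in the reverse Kaplan-Meier calculation.

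**The concern.** The reverse Kaplan-Meier method estimates how long patients would have been followed had nobody died. It swaps the usual roles: reaching the date of last news alive is the event, and death is a censoring. A patient who dies at 40 months therefore still counts in the risk set when others reach their last news at 28 or 35 months. If the deceased are filtered out first, the method is named but the observations that distinguish it from an ordinary median are gone.

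A programmer who follows 7.2.2 to the letter would filter on vital status. The reported follow-up would then describe survivors only. It would tend to be too short, would fall as mortality rises, and would have a confidence interval based on survivors alone. A programmer who follows 7.2.1 and 6.5 would keep everyone.

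**Working it through.** The documents state no follow-up figure, so there is none to reproduce. The check has three steps.

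**1. What the literal instruction computes.** With *k* living patients at distinct times and no censoring, the Kaplan-Meier product after the *j*-th patient telescopes:

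(k−1)/k × (k−2)/(k−1) × … × (k−j)/(k−j+1) = (k−j)/k.

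This first reaches 0.5 or less at j = k/2, rounded up, which is the (lower) sample median. A numerical comparison in 2,000 random data sets found no mismatch.

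**2. Direction.** Removing the deceased leaves the number of events at each last-news date unchanged and can only shrink the number at risk. Each factor 1 − d/n is therefore equal or smaller, the curve is equal or lower, and the median is equal or earlier. The two versions differ when some deaths occur after the earliest last-news dates, as staggered entry makes likely.

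**3. Size.** Inputs from the documents:

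- Synopsis calendar: inclusion April 2013 to April 2016 (36 months), end July 2018 (27 months later). Potential follow-up runs from a = 27 to b = 63 months.
- Protocol XII.1 calendar: inclusion April 2013 to April 2015 (24 months), end July 2017 (27 months later). Potential follow-up runs from a = 27 to b = 51 months.
- SAP 4.3: "58 patients were to be included".

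Assumptions not in the documents: uniform accrual, exponential overall survival with median M of 24 to 36 months, no loss to follow-up, data cut-off at end of study.

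The full reverse Kaplan-Meier targets the median potential follow-up, (a + b)/2: (27 + 63)/2 = 45 and (27 + 51)/2 = 39 months.

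Among survivors, potential follow-up c has density proportional to 2^(−c/M) on [a, b]. Its median is

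m = −M × log2{[2^(−a/M) + 2^(−b/M)]/2},

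and the surviving fraction is

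p = (M/ln 2) × [2^(−a/M) − 2^(−b/M)]/(b − a).

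| Calendar | M | 2^(−a/M) | 2^(−b/M) | m (months) | Full | Shortfall | p | 58 × p |
|---|---|---|---|---|---|---|---|---|
| Synopsis | 24 | 0.4585 | 0.1621 | 40.5 | 45 | 4.5 | 29% | 16.5 |
| Synopsis | 36 | 0.5946 | 0.2973 | 41.9 | 45 | 3.1 | 43% | 24.9 |
| XII.1 | 24 | 0.4585 | 0.2293 | 37.0 | 39 | 2.0 | 33% | 19.2 |
| XII.1 | 36 | 0.5946 | 0.3746 | 37.6 | 39 | 1.4 | 48% | 27.6 |

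First row worked through: (0.4585 + 0.1621)/2 = 0.3103; log2 of this is −1.688; 24 × 1.688 = 40.5.

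**Sensitivity.** A simulation with 58 patients and an assumed median survival of 15 to 40 months gave these mean shortfalls:

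- No loss to follow-up: 1.3 to 3.6 months (XII.1 calendar) and 3.1 to 7.4 months (synopsis calendar).
- Loss of 5 to 10% per year, with lost patients counted as living: 2.1 to 10.7 and 4.2 to 15.9 months.

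The upper ends combine the shortest survival with the heaviest loss.

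**The case against.** The strongest reply is that the parenthesis is a gloss, not a filter. In reverse Kaplan-Meier the living patients are the events, so describing the result as relating to them is loose but understandable. The surrounding text supports this. The next sentence names the inverse method, 7.2.1 gives the deceased a follow-up time that would be pointless if they were dropped, and SAP 6.5 and Protocol XII.4 are unrestricted. On this reading the intended estimate is correct and only the wording is faulty. The argument has weight, and the documents do not show a deliberate decision to exclude the deceased. It does not make the sentence safe: its plain meaning is a restriction, and no event and censoring coding is given elsewhere to settle the matter.

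The size is also open to challenge. The documents give no assumption for overall survival or its distribution, and no data cut-off date (SAP 4.4 says only that a single final analysis is planned). The gap on the XII.1 calendar is under half of that on the synopsis calendar. This stands, so both calendars are shown and the figures are conditional.

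A reader might infer three stronger claims that the documents do not support:

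- *That two SAP sections yield two different values.* Section 7.2.1 defines the interval and names no estimator; only 7.2.2 describes the calculation.
- *That the plan uses median follow-up as its declared measure of maturity for progression-free and overall survival.* It does not say so. Section 7.2 treats it as a monitoring characteristic, and the section 7 table lists it with the baseline descriptions.
- *That efficacy conclusions are at risk.* The primary endpoint is at 9 months and the listed rates for progression-free and overall survival stop at 18 months, while the shortest potential follow-up on either calendar is 27 months.

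**Conclusion.** The point holds as a wording fault that would produce a wrong descriptive number if followed to the letter. The reduction to the survivors' plain median and the direction of the error need no distributional assumption. The size does: under the stated assumptions the reported median would be about 3 to 4.5 months too short on the synopsis calendar and about 1.4 to 2 months on the XII.1 calendar. Its confidence interval would rest on 29 to 48% of patients across the two calendars. If the parenthesis is only a gloss, the number will be right and just the text needs correcting.

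The consequence ends with the follow-up figure and its interval. The primary endpoint, the 33-of-48 decision rule and the estimates of progression-free and overall survival do not change. This is a minor improvement.

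**What to change.** In SAP 7.2.2, delete the parenthesis that refers to living patients. Add a sentence such as: *All patients of the analysed population enter the reverse Kaplan-Meier estimate; those alive or lost to follow-up count as events at the date of last news, and those who died are censored at the date of death.* Naming patients lost to follow-up also removes any doubt about whether they count as living, since 7.2.1 lists them separately.

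The same sentence serves all three populations in the section 7 table and aligns 7.2.2 with 7.2.1, 6.5 and Protocol XII.4. The cost is one line of SAP text, with no new data and no change to any efficacy analysis. SAP 4.5 requires changes to the plan to be made before the database is frozen.

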7.3 Evaluation of the primary efficacy endpoint

Population: ITTm

7.3.1 Definition of the primary endpoint

The primary endpoint is to evaluate the rate of patients alive without progression at 9 months after the start of treatment. Progression is defined as radiological progression according to RECIST V1.1 criteria, as assessed by the investigator.

Patients who progressed or died (from any cause) within 9 months of initiation of therapy (Day 1 of Cure 1) will be considered to have failed the primary endpoint at 9 months.

The scans selected for analysis will be the scans before and up to 9 months with a +/- 1 month window.

Patients without a 9-month evaluation will be reviewed according to the following rules:

- If the patient has a late assessment (10 months or more) and is not progressing at that time, then they will be considered progression-free at 9 months.
- If the patient has documented progression at more than 9 months without imaging at 9 months, then that patient will be considered to be in progression at 9 months. If progression is documented at more than 11 months, the patient will not be considered to be in progression at 9 months.
- If progression is documented before the 9-month assessment, the patient is considered to be in progression at 9 months.

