5.1.2 Modified intention-to-treat (mITT) population - evaluable patients

The modified intention-to-treat population is defined as all **evaluable** included patients, regardless of their eligibility criteria and treatment received.

A patient is considered evaluable if:

- he had a chemoembolization and
- received at least one cycle of chemotherapy and
- at least one assessment during the 9 months of follow-up was done

A listing of patients excluded from the ITTm population will be provided with the reasons for exclusion.

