7.3.2 Evaluation of the primary endpoint

The primary endpoint will be assessed on the ITTm population. This criterion will be described according to the usual descriptive statistics. A one-sided 95% confidence interval will be calculated using the exact method.

The decision rules to be applied on 48 patients evaluable in the analysis (ITTm population) are:

- If 32 or fewer patients are alive without progression, then the treatment is considered ineffective.
- If 33 or more patients are alive without progression, then the treatment is considered effective.

These may be adjusted based on the actual number of evaluable patients included.

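### For patients without a 9-month evaluation, SAP 7.3.1 scores progression first seen after 11 months as success at 9 months, whatever the date of the last clean scan

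*SAP*

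**What the plan says.** The primary endpoint is binary. SAP 7.3.2 applies a count to the evaluable (ITTm) patients: "If 33 or more patients are alive without progression, then the treatment is considered effective", on 48 evaluable patients.

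SAP 7.3.1 sets status at 9 months as follows.

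- **General rule.** Patients who progress or die "within 9 months of initiation of therapy (Day 1 of Cure 1) will be considered to have failed the primary endpoint".
- **Scans used.** "The scans selected for analysis will be the scans before and up to 9 months with a +/- 1 month window", which I read as months 8 to 10.
- **Fallback rules, only for patients without a 9-month evaluation:**
  - Rule 1: a clean assessment at 10 months or later makes the patient progression-free at 9 months.
  - Rule 2, first sentence: "If the patient has documented progression at more than 9 months without imaging at 9 months", the patient is a failure.
  - Rule 2, second sentence: "If progression is documented at more than 11 months, the patient will not be considered to be in progression at 9 months".
  - Rule 3: progression documented before the 9-month assessment is a failure.

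Three other provisions matter. SAP 5.1.2 makes a patient evaluable after chemoembolization and one cycle of chemotherapy if "at least one assessment during the 9 months of follow-up was done". SAP 6.3 states: "Except in the cases specified, missing data will not be replaced". Protocol VII schedules imaging at D63-D70 and two-monthly thereafter.

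**The concern.** The second sentence of rule 2 looks only at when progression was found, not at when the patient was last known to be clean. A patient clean at 7.5 months and found progressing at 10.5 months is a failure. A patient clean at 2 months and found progressing at 11.5 months is a success. The second patient was observed less and gets the better result.

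The rule feeds the only analysis that decides the trial, where 33 of 48 is effective and 32 of 48 is not. The trial is open-label with an investigator-assessed endpoint, so status rules should be complete and should not reward missed imaging.

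A related silence supports the point. A living patient with one early clean scan and no later information is evaluable under SAP 5.1.2 but matches no rule in 7.3.1. The analysis is a count with an exact interval, so censoring does not resolve the case.

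**Working it through.** **1. The plan's own figures.** Inputs from SAP 4.3: one-sided 5%, power 90%, 55% versus 75%.
- n = [(1.645·√(0.55·0.45) + 1.282·√(0.75·0.25)) / 0.20]² = 47.1, so 48.
- Cut-off: 48·0.55 + 1.645·√(48·0.55·0.45) = 32.07, so 33.
- Exact binomial: P(X≥33 | 48, 0.55) = 3.7%; P(X≥33 | 48, 0.75) = 87.7%.

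The sample size and cut-off reproduce. The exact values are the reference below.

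**2. Whom the sentence reaches.** A clean scan at 8-10 months is a 9-month evaluation, so the fallback rules do not apply. A clean scan at 10 months or later is already a success under rule 1. The sentence therefore gives an unsupported success only where there is no clean scan from month 8 on. On the two-monthly calendar such a patient missed the scans due near months 8 and 10 and was last clean at about month 6 or earlier.

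**3. Chance that progression preceded month 9.** Assume a constant hazard, S(t) = 0.55^(t/9), and progression seen at 11.5 months, with S(11.5) = 0.4658. For last clean scan L the chance is [S(L) − S(9)] / [S(L) − S(11.5)].

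| L (months) | Numerator | Denominator | Chance |
|---|---|---|---|
| 6 | 0.1213 | 0.2054 | 59% |
| 4 | 0.2167 | 0.3008 | 72% |
| 2 | 0.3256 | 0.4097 | 79% |

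The sentence scores all of these patients as successes.

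**4. Effect on the decision rule.** Let g be the share of patients with no scan from month 6 to month 12 (assumed; not in the documents). Under H0, S(6) − S(9) = 0.1213 and S(9) − S(12) = 0.0994. Of progressions in that gap, 0.0994/0.2207 = 45% come after month 9 and are true successes.
- As written, the success rate is 0.55 + 0.1213g.
- With these patients counted as failures, it is 0.55 − 0.0994g. At a true 75%, S(9) − S(12) = 0.0686, so the rate is 0.75 − 0.0686g.

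| g | Wrong successes in 48 (48·g·0.1213) | Level as written | Level if counted as failures | Power if counted as failures |
|---|---|---|---|---|
| 5% | 0.3 | 4.4% | 3.2% | 86.5% |
| 10% | 0.6 | 5.3% | 2.7% | 85.2% |
| 20% | 1.2 | 7.3% | 2.0% | 82.5% |

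If 10% of the events are deaths (assumed), which remain failures, replace 0.1213 by 0.9·0.1213: the level as written is 5.1% or 6.9% at g = 10% or 20%.

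The level reaches 5% at a success rate of 0.5603, so g = 0.0103/0.1213 = 8.5%, about 4 of 48. With a last clean scan at month 4 it is 0.0103/0.2167 = 4.8%, about 2 of 48.

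**5. The opposing rule.** Progression found at 9-11 months without a 9-month scan is a failure, though some of it began after month 9. For an assumed gap from month 6 to 10.5, S(9) − S(10.5) = 0.0522. If 10% or 20% of patients had that gap, the level would fall to 3.1% or 2.7%.

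**6. Patients with only early clean scans.** Let k of the 48 have no stated status, unrelated to outcome (k assumed).

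| k | Level, all success | Level / power, all failure | Excluded: cut-off, level / power |
|---|---|---|---|
| 1 | 4.7% | 2.4% / 82% | 32/47, 4.7% / 89% |
| 2 | 6.0% | 1.5% / 76% | 32/46, 3.2% / 85% |
| 3 | 7.6% | 0.9% / 67% | 31/45, 4.1% / 87% |

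On a fixed 48, the choice between success and failure decides the verdict if 33−k ≤ X ≤ 32 among the other 48−k patients. At a true rate of 65% that probability is 11%, 22% or 32%.

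**The case against.** **The sentence does useful work.** Suppose a patient misses the month-8 scan, is clean at 10.2 months and progresses at 12.2. Rule 1 says success; the first sentence of rule 2, read literally, says failure. The 11-month sentence resolves this correctly, and deleting it would leave the two rules in conflict. This stands and shapes the fix.

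**The harm rests on an undocumented rate.** Patients on FOLFOX are examined before every two-weekly cycle, and nothing in the documents supports 10% or 20% with a six-month imaging gap. This stands: the figures are a sensitivity range, not a forecast.

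**The bias is not all one way.** Step 5 shows an offset, and failure coding has its own error: at g = 10% the text as written miscounts 0.6 of 48 patients as successes, while the fix miscounts 48·0.10·0.0994 = 0.5 true successes as failures. This stands too, and is why the alternative coding should be reported. It does not justify a rule that improves a patient's result as the gap lengthens.

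**The plan allows for losses and for other analyses.** SAP 4.3 says: "Taking into account a 20% rate of patients lost to follow-up or not evaluable, 58 patients were to be included", and the cut-off may be adjusted to the number evaluable. But SAP 5.1.2 does not remove a patient lost after one clean scan, and adjusting the cut-off assigns no status. The ITT, per-protocol and Kaplan-Meier analyses would help to show fragile coding, but they do not govern the decision.

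**Conclusion.** The concern holds for patients without a 9-month evaluation and with no clean scan in or after the window. For them the sentence credits an interval in which progression more likely than not preceded month 9 (59% to 79% under the assumptions of step 3). The level would move from 3.7% to 4.4%, 5.3% or 7.3% for assumed gap rates of 5%, 10% or 20%, before any offset from the 9-11 month rule. The rule should be corrected; the size of its effect in this trial is unknown.

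A reader might infer more than the documents support:

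- That the sentence affects every patient progressing after 11 months. It sits under the fallback rules, so a patient with a clean scan at 8-10 months is untouched.
- That the type I error exceeds 5%. That needs more than about 4 of 48 patients with a month 6-12 gap, or about 2 of 48 if the last clean scan is at month 4. No such rate is given.
- That 7.3.1 as a whole favours the treatment. Rule 1 is sound, and the 9-11 month rule works against the treatment.
- That patients with only early clean scans will be counted as successes. The SAP assigns them no result. This is missing detail that supports the point but does not carry it.

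**What to change.** In SAP 7.3.1, before database freeze (SAP 4.5 provides for changes up to then):

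1. Keep the 11-month sentence only for patients with a clean scan in or after the 8-10 month window, and state that rule 1 governs a patient clean at 10 months or later who progresses afterwards.
2. Count a patient with no scan in the window whose next scan shows progression as a failure in the primary analysis. Report a sensitivity analysis that counts these patients as successes.
3. State one coding for evaluable patients with only early clean scans and no later status, and report how many there are. Either keep them in the denominator as failures, or exclude them and re-derive the cut-off. Give the other as a sensitivity analysis.

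The cost is a few sentences, two sensitivity analyses and a possibly less favourable rate. For item 2, power is about 85% or 83% instead of 87.7% if 10% or 20% of patients had a month 6-12 gap. For item 3 with 1, 2 or 3 such patients, failure coding gives power of 82%, 76% or 67%. Exclusion gives 89%, 85% or 87%, with an exact level of at most 4.7%, but assumes that missing status is unrelated to outcome.
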